### **9.2.2. Adverse Event Summaries**

An overall summary of AEs by treatment group will include the following:

- Number (%) of participants reporting any TEAEs
- Number (%) of participants reporting any serious TEAEs
- Number (%) of participants reporting any Grade 3 or higher TEAEs
- Number (%) of participants reporting any treatment-related TEAEs
- Number (%) of participants who temporarily interrupted study drug because of TEAEs
- Number (%) of participants who permanently discontinued study drug because of TEAEs
- Number (%) of participants who had any fatal TEAE

The following summaries will be produced by MedDRA term (if 2 or fewer participants appear in a table, a listing may be appropriate):

- Summary of TEAEs by SOC and PT
- Summary of TEAEs by SOC and PT
- Summary of TEAEs by PT in decreasing order of frequency
- Summary of Grade 3 or higher TEAEs by SOC and PT
- Summary of serious TEAEs by SOC and PT
- Summary of treatment-related TEAEs by SOC and PT
- Summary of TEAEs with a fatal outcome by SOC and PT
- Summary of TEAEs leading to dose interruption of study drug by SOC and PT
- Summary of TEAEs leading to discontinuation of study drug by SOC and PT

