### **5.2. Treatment Groups**

This is a Phase 3, multicenter, randomized, double-blind, placebo-controlled study to evaluate the efficacy and safety of parsaclisib 2.5 mg QD. Data will be summarized based on the actual treatment that the participant received at Day 1.

Unless other specified, the treatment groups will be parsaclisib 2.5 mg QD and placebo QD. For exposure, compliance, and adverse events, the treatment groups will be placebo QD, placebo QD to parsaclisib 2.5 mg QD, and parsaclisib 2.5 mg QD.

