## **6.2. Disposition of Participant**

The number and percentage of participants who were enrolled, who were randomized (double-blind period only), who were treated, and who completed treatment for each period will be summarized for the safety populations.

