## **6.4. Exposure**

For participants in the safety population, exposure will be summarized descriptively for duration of treatment, average daily dose, and total dose. The treatment groups will be provided based on the actual treatment received (see Section [5.2](#)).

Duration of treatment with study drug is defined as the number of days from Day 1 to the date of last record of study drug administration. In addition, daily usage of prednisone (or equivalent) will be summarized using descriptive statistics.

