### 9.1. General Considerations

Analyses in this section will be provided for the safety population. Treatment groups will be provided based on the actual treatment received (see Section 5.2). For participants who cross over treatments, the date of first dose is treatment-specific; the end date will be either 30 days after the date of the last dose of this treatment or the date of the first dose in the next treatment, whichever comes first. Analysis of AEs will be limited to TEAEs, but data listings will include all AEs regardless of their timing in relation to study drug administration. Summary tables may be replaced with listings when appropriate. For instance, an AE frequency table may be replaced with a listing if it only contains a few unique PTs reported on relatively few participants.

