### 9.2. Adverse Events

#### 9.2.1. Adverse Event Definitions

A TEAE is any AE either reported for the first time or worsening of a pre-existing event after first dose of study drug and within 30 days of the last dose of study drug. Analysis of AEs (as discussed below) will be limited to TEAEs, but data listings will include all AEs regardless of their timing in relation to study drug dose administration.

Adverse events will be tabulated by MedDRA PT and SOC. Severity of AEs will be graded using the National Cancer Institute CTCAE v5. The CTCAE reporting guidelines and grading details are available on the Cancer Therapy Evaluation Program website.

The subset of AEs considered by the investigator to be related to study drug will be considered treatment-related AEs. If the investigator does not specify the relationship of the AE to study drug, the AE will be considered to be treatment-related. The incidence of AEs and treatment-related AEs will be tabulated. Serious AEs will also be tabulated.

Any missing onset date, causality, or severity must be queried for resolution. Unresolved missing causality and severity will be handled according to the following rules:

- An unresolved missing causality will be considered treatment-related.
- An unresolved missing severity will be identified as an unknown severity.

For purposes of analysis, all AEs will be considered TEAEs unless the AE can unequivocally be defined as not treatment-emergent.

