## APPENDIX A. PLANNED TABLES AND LISTINGS

This appendix provides a list of the planned tables and listings for the Clinical Study Report. Shells are provided in a separate document for tables that are not in the most current Standard Safety Tables v1.13.

The list of tables and listings are to be used as guidelines. Modifications of the lists that do not otherwise affect the nature of the analysis will not warrant an amendment to the SAP.

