### Tables

Table No.	Title	Population	Standard
Baseline and Demographic Characteristics			
1.1 Disposition			
1.1.1	Analysis Populations	Safety	X
1.1.2	Summary of Participant Disposition	Safety	X
1.2 Demography			
1.2.1	Summary of Demographics	Safety	X
1.3 Baseline Characteristics			
1.3.1	Summary of Baseline Disease Characteristics	Safety	X
1.4 Prior Medication and Concomitant Medication			
1.4.1	Summary of Prior Medications	Safety	X
1.4.2	Summary of Prior Medications for wAIHA	Safety	X
1.4.3	Summary of Concomitant Medications	Safety	X
1.5 Others			
1.5.1	Summary of General Medical History	Safety	X
1.5.2	Summary of wAIHA History	Safety	X
1.5.3	Summary of Protocol Deviations by Category	Safety	X
Efficacy			
2.1 Primary and Key Secondary Efficacy			
2.1.1	Summary of Participants With Hemoglobin $\geq 10$ g/dL With an Increase From Baseline of $\geq 2$ g/dL	Safety	
2.1.2	Summary of Participants With a $\geq 3$ -Point Increase From Baseline in FACIT-F Score at Week 24	Safety	
Safety			
3.1 Study Drug Exposure			
3.1.1	Summary of Drug Compliance	Safety	X
3.1.2	Summary of Study Drug Exposure	Safety	X
3.1.3	Summary of Daily Usage of Prednisone	Safety	X
3.2 Adverse Events			
3.2.1	Overall Summary of Treatment-Emergent Adverse Events	Safety	X
3.2.2	Summary of Treatment-Emergent Adverse Events by MedDRA System Organ Class and Preferred Term	Safety	X
3.2.3	Summary of Treatment-Emergent Adverse Events by MedDRA Preferred Term in Decreasing Order of Frequency	Safety	X
3.2.4	Summary of Treatment-Related Treatment-Emergent Adverse Events by MedDRA System Organ Class and Preferred Term	Safety	X

Table No.	Title	Population	Standard
3.2.5	Summary of Grade 3 or Higher Treatment-Emergent Adverse Events by MedDRA System Organ Class and Preferred Term	Safety	X
3.2.6	Summary of Treatment-Emergent Adverse Events With a Fatal Outcome by MedDRA System Organ Class and Preferred Term	Safety	X
3.2.7	Summary of Serious Treatment-Emergent Adverse Events by MedDRA System Organ Class and Preferred Term	Safety	X
3.2.8	Summary of Treatment-Emergent Adverse Events Leading to Dose Interruption by MedDRA System Organ Class and Preferred Term	Safety	X
3.2.9	Summary of Treatment-Emergent Adverse Events Leading to Discontinuation of Study Drug by MedDRA System Organ Class and Preferred Term	Safety	X
3.3 Laboratory			
3.3.1	Summary of Laboratory Values - Hematology	Safety	X

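### The adverse event tables are crude percentages with no double-blind-period version, so the parsaclisib column can pool more time at risk than placebo; a cheap, minor improvement

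*SAP*

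**What the plan says.** SAP 9.2.2 plans adverse event summaries by treatment group as numbers and percentages of participants: "Number (%) of participants reporting any TEAEs", then serious, Grade 3 or higher, related, interruption, discontinuation and fatal events. Appendix A turns these into Tables 3.2.1 to 3.2.9, beginning with "Overall Summary of Treatment-Emergent Adverse Events". No title names a study period or a rate per unit of time.

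SAP 9.2.1 counts an event as treatment-emergent if it starts or worsens "after first dose of study drug and within 30 days of the last dose of study drug". SAP 5.2 sets the columns: "For exposure, compliance, and adverse events, the treatment groups will be placebo QD, placebo QD to parsaclisib 2.5 mg QD, and parsaclisib 2.5 mg QD". For participants who cross over, SAP 9.1 makes the window treatment-specific, ending 30 days after the last dose of that treatment or at "the date of the first dose in the next treatment, whichever comes first".

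Two other sections bear on this. In SAP 6.4, "exposure will be summarized descriptively for duration of treatment, average daily dose, and total dose", in a table separate from the event tables. In SAP 6.2, the number of participants "who completed treatment for each period will be summarized for the safety populations", so disposition is split by period where adverse events are not.

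**The concern.** A crude percentage depends on how long participants are watched as well as on the treatment. For someone who starts on parsaclisib there is no next treatment to close the window under SAP 9.1, and SAP 9.2.1 has no cut at Week 24. The window can run through the double-blind period, the open-label period and the extension. Placebo treatment lasts at most 24 weeks, and Protocol Amendment 2 lets placebo participants move to parsaclisib sooner (Protocol 4.1).

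With efficacy testing dropped, the safety tables are a main remaining output of the study. Placed side by side, the columns invite a reading that mixes drug effect with time at risk.

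A smaller gap sits beside this. SAP 9.1 implies that a crossover participant's events before the switch belong to placebo, but SAP 5.2 names both a placebo column and a placebo-to-parsaclisib column without saying which one holds them.

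**Working it through.** The plan gives no adverse event incidence and no exposure figure, so there is nothing of its own to reproduce here. Its one design calculation, power for the primary endpoint, does not bear on this point.

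**Time at risk by design** (Protocol Section 1, Table 2)
- Placebo: at most 24 weeks on treatment, or less with early crossover.
- Parsaclisib: 24 weeks double-blind + 24 weeks open-label = 48 weeks, a ratio of 48/24 = 2.0. Adding about 104 weeks of extension gives 152 weeks, a ratio of 152/24 = 6.3. These are maxima, not expected values.

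**Effect on a crude percentage.** Assume the same constant hazard in both arms and let p be the 24-week incidence. The risk over T weeks is 1 − (1 − p)^(T/24).

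| p at 24 weeks (assumed) | 12 weeks | 24 weeks | 48 weeks |
|---|---|---|---|
| 10% | 5.1% | 10% | 1 − 0.9² = 19% |
| 20% | 10.6% | 20% | 1 − 0.8² = 36% |
| 40% | 22.5% | 40% | 1 − 0.6² = 64% |

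**Effect of early stops on parsaclisib.** Assume 9 parsaclisib and 4 placebo participants, p = 40%, placebo followed for 24 weeks, and no 30-day tail.
- All 9 reach Week 48: 64% against 40%.
- 3 stop at Week 12 and 6 reach Week 48: (3 × 22.5 + 6 × 64)/9 = 50% against 40%.
- 4 stay 12 weeks, 2 stay 24 and 3 stay 48: (4 × 22.5 + 2 × 40 + 3 × 64)/9 = 40% against 40%.
- If the rest reach Week 48, the gap is zero when a share s stops at Week 12, where s = (64 − 40)/(64 − 22.5) = 58%. For p = 10%, s = (19 − 10)/(19 − 5.1) = 65%.

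**Effect of early crossover.** If 2 of 4 placebo participants cross at Week 12, the placebo percentage is (2 × 22.5 + 2 × 40)/4 = 31% instead of 40%. Time at risk is then unequal even inside the double-blind period, so a period cut alone does not equalise it.

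**The 30-day tail.** Under Amendment 2 (Protocol 4.1, 7.1.2 and 8.10), a participant on placebo who stops has the final visit at discontinuation and no follow-up visit. A participant on parsaclisib who stops has one follow-up visit about 4 weeks after the last dose. Events in the tail are therefore not looked for equally. Counting the tail as time at risk would also put poorly observed placebo time in the denominator. For a Week 12 stop, 12/(12 + 4.3) = 0.74, so a placebo rate could be understated by up to 26%.

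**Precision of a rate.** Four placebo participants over 24 weeks give 96/52.18 = 1.84 patient-years. One event gives 1/1.84 = 0.54 per patient-year, exact Poisson 95% CI 0.01 to 3.03.

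**The case against.** The case against acting is reasonable, and much of it stands.

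- **Nothing is tested on these tables.** SAP 11.1 rules out p-values and statistical comparisons, although in a paragraph about efficacy endpoints. Protocol 10.3.3 planned tabulation only and never promised rates. This limits the importance; it does not make the columns comparable.
- **Exposure is disclosed.** Duration is summarised in the same three groups, listings include all events whatever their timing, and SAP 9.1 and 9.2.2 let listings replace sparse tables. A careful reader could work out the time at risk. None of this changes the percentages.
- **Chance dominates.** In the 9:4 illustration at 40%, a gap of 24 points or more in either direction has probability 0.42 with equal time and 0.45 when 3 of 9 stop at Week 12. The probability of such a gap against parsaclisib does rise, from 0.20 to 0.32.
- **A rate adds little.** It is very imprecise here and removes the effect of unequal time only if the hazard is roughly constant. Protocol 2.2.2 mentions late-onset events, so that cannot be taken for granted. This stands, and a formal rate should be optional.
- **The layouts were not seen.** Appendix A states: "Shells are provided in a separate document for tables that are not in the most current Standard Safety Tables v1.13". The event tables are marked as standard, so their headers could not be checked. The titles and the text of SAP 9.2.2 show no period split.

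SAP 9.2.2 lists the system organ class and preferred term summary twice, and a reader might take one as a double-blind version. Appendix A has a single such table (3.2.2), so the duplicate does not support that.

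**Conclusion.** The omission is real and worth correcting, but minor. The visible SAP text has crude percentages and no double-blind-period event table, and the design allows the parsaclisib column to carry more time at risk than placebo.

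Two stronger readings are tempting and are not supported. A reader might infer that parsaclisib's event percentages will be inflated, perhaps in line with the 6.3-fold design maximum. The documents give no arm split, discontinuation, crossover or exposure data for the 13 treated participants. Even from March 2022 to the SAP date of 17 January 2024 is only about 98 weeks, and early stops or rollover could shorten parsaclisib time until the gap vanishes. A reader might also infer that events after crossover are charged to placebo. SAP 9.1 ends the placebo window at the first parsaclisib dose, so they are not.

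All the percentages above rest on an assumed equal constant hazard, assumed incidences and assumed stopping patterns. They show that the distortion is possible and how large it could be; they do not show that it occurred.

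**What to change.** In SAP 5.2, 9.2.2 and Appendix A:

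1. Add an overall treatment-emergent event summary and one system organ class and preferred term table for the double-blind period, by treatment received on Day 1. Run the window from first dose to the earlier of the first open-label parsaclisib dose or the last double-blind dose, and count crossovers' time before the switch under placebo. Report events in the 30 days after stopping separately. Note that under Amendment 2 ascertainment there differs by arm, because only parsaclisib stoppers have a follow-up visit.
2. Label any table of all parsaclisib exposure as non-comparative.
3. Show total patient-years on treatment in each adverse event column header, because early crossover leaves time unequal even within the double-blind period. An exposure-adjusted rate is optional. If given, it should use on-treatment time only and state the constant-hazard assumption and the imprecision.
4. State in SAP 5.2 which column holds crossovers' events before the switch, consistent with SAP 9.1.

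The cost is a few extra sparse tables, a header line and one clarifying sentence, all from data already collected, with no added participants or procedures. The new percentages will be very imprecise. The change removes an avoidable distortion; it does not make the comparison informative.

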## 9.3. Clinical Laboratory Tests

### 9.3.1. Laboratory Value Definitions

Laboratory values and change from baseline will be summarized descriptively by central laboratory. Baseline will be determined according to Section 4.1.3, with exceptions listed below, in which case the investigative site laboratory or an accredited local laboratory may be used:

- Hematology panels (ie, complete blood count and differential count), will be sent to a local laboratory for analysis.
- Participant management, which includes dose modification, serious adverse event, or COVID-19 restrictions (eg, travel), for local laboratory assessments deemed necessary by the investigator for participant management. Note: Such assessment data and reference ranges must be recorded in the participant's eCRF.

In the event both local and central laboratory assessments are available, local laboratory assessment will be used for analysis. Laboratory values, change from baseline values, and percent change from baseline values will be summarized descriptively by visit. Baseline values will be determined using the nonmissing values collected before the first administration, prioritizing scheduled assessments over unscheduled visits. For baseline laboratory values with the same date and time in the same priority category, additional rules may be provided following consultation with the medical monitor to delineate the value that will be defined as baseline.

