8.4.5. Laboratory Assessments

See Table 11 for the list of clinical laboratory tests to be performed and Table 3, Table 4, and Table 5 for the timing and frequency. A central laboratory will perform all clinical laboratory assessments for safety (ie, blood chemistries, hematology assessments, coagulation tests, endocrine function, and urinalysis). Additional testing may be required by the sponsor based on emerging safety data. All Protocol-required laboratory assessments must be conducted in accordance with the Laboratory Manual and Table 3, Table 4, and Table 5.

Note: The participants' screening hemoglobin enrollment eligibility will be based on a local laboratory assessment. Additionally, if the central laboratory is unable to perform any other required screening tests due to hemolysis related to wAIHA or the analytical method, then local laboratory test results may be used to determine participant eligibility.

At-home blood collection will be conducted during remote visits, except for countries where remote visits are not permitted by local laws and/or regulations (see Table 3 and Table 4). At-home sampling for additional laboratory assessments may also be conducted, except for countries where remote visits are not permitted by local laws and/or regulations; see Appendix B for COVID-19—related guidance. Information regarding collection, processing, and shipping of samples for laboratory assessment is provided in the Laboratory Manual.

Clinically significant abnormal laboratory findings are those that are not associated with the underlying disease, unless judged by the investigator to be more severe than expected for the participant's condition. All laboratory tests with values considered clinically significantly abnormal during participation in the study or within 30 days after the last dose of study drug should be repeated until the values return to normal or baseline or are no longer considered clinically significant by the investigator or medical monitor.

If screening laboratory assessments are performed more than 32 days before Day 1, then the tests must be repeated and eligibility confirmed before study drug administration on Day 1.

Laboratory sample collection on Day 1 must be performed before study drug administration.

See Section 9.1 for information regarding laboratory abnormalities that should be recorded as an AE in the eCRF.

Table 11: Required Laboratory Analytes

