### 9.3.2. Laboratory Value Summaries

Clinical laboratory tests, including hematology, serum, and chemistry, will be performed for each participant per the schedule of assessments. If specific safety issues arise, additional unscheduled laboratory tests/analyses will be performed at the discretion of the investigator.

All test results and associated normal ranges from central laboratories will be reported in SI units. All tests with numeric values will have a unique unit per test.

For test results that will be summarized with available normal ranges, the number and percentage of participants with the laboratory values being low, normal, high, and missing will be tabulated for each test and each visit.

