### 11.1. Changes to Protocol-Defined Analyses

On 17 APR 2023, Incyte decided to terminate this Phase 3 study. The decision was based on change in the regulatory landscape for Pi3k-delta inhibitors combined with enrollment challenges.

With limited enrollment in each treatment group, as well as participant option for early crossover (to parsaclisib), most of the Protocol-defined statistical analyses on efficacy endpoints will not be applicable; therefore, summary statistics will only be provided for hemoglobin response and FACIT-F scores and listings will only be provided for all other efficacy endpoints. Additionally, no p-values will be provided and no statistical comparisons will be made.

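### Do the SAP's laboratory-source rules (local result preferred over central, hematology sent to local laboratories) need to change?

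*SAP*

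**What the plan says.** SAP 9.3.1 begins with a default: "Laboratory values and change from baseline will be summarized descriptively by central laboratory". It then names two situations in which a site or accredited local laboratory may be used:

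- Hematology panels, which "will be sent to a local laboratory for analysis".
- "Participant management, which includes dose modification, serious adverse event, or COVID-19 restrictions", meaning tests the investigator finds necessary. A note to this item adds: "Such assessment data and reference ranges must be recorded in the" participant's eCRF.

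After the list comes the rule for duplicates: "In the event both local and central laboratory assessments are available, local laboratory assessment will be used for analysis". It names no analyte, visit or reason.

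SAP 9.3.2 says "All test results and associated normal ranges from central laboratories will be reported in SI units". It also requires a single unit for each numeric test, and it tabulates low, normal, high and missing wherever normal ranges are available. Neither of those two rules is confined to central results.

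Protocol 8.4.5 states: "A central laboratory will perform all clinical laboratory assessments for safety (ie, blood chemistries, hematology assessments", followed by coagulation, endocrine function and urinalysis. Table 11 of the protocol attaches two footnotes to its hematology column. Footnote a, which also covers chemistry, allows real-time management by local laboratory; footnote b ties panels to the site's standard of care. Protocol 8.2.1 accepts local results for immediate management.

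SAP 11.1, on changes to protocol-defined analyses, says that "most of the Protocol-defined statistical analyses on efficacy endpoints will not be applicable" and drops p-values and comparisons. It does not mention laboratories.

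**The concern.** There are two apparent conflicts.

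**Chemistry.** A section that promises central-laboratory summaries goes on to say that a local result displaces a central one. Chemistry Table 3.3.2 could then hold a mixture, and a change from baseline could subtract a central value from a local one. The switching would not be random. The SAP links local testing to dose modification, serious adverse events and COVID-19 restrictions, so it would tend to fall on participants who are being managed for something.

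**Hematology.** The two documents name different laboratories for the same panels. SAP 9.3.2 mentions normal ranges only in its sentence about central laboratories, and the instruction to record local ranges sits under the participant-management item. It is therefore not stated whose ranges classify values in Table 3.3.1.

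At stake would be the labeling and reading of the two laboratory tables.

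**Working it through.** The plan gives no figure to reproduce here. The check has four parts.

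**1. Reach of the rules.** Inputs are 13 randomized and treated participants (SAP section 1) and the post-baseline double-blind visits in Protocol Table 3.

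- Serum chemistry is due at Weeks 4, 8, 12, 16, 20 and 24, which is 6 visits: 13 × 6 = 78 participant-visits.
- Hematology is due at the same 6 visits plus Weeks 2, 6 and 10, which is 9 visits: 13 × 9 = 117. Amendment 2 drops the 3 extra visits: 13 × (9 − 3) = 78.

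These are ceilings for the double-blind period because they ignore dropout and early crossover. Chemistry and hematology continue in the open-label and extension periods, so they do not bound the rules' full reach. They also do not count affected values, since the tie-break operates only where both a local and a central result exist. Weekly repeat ALT/AST during a drug interruption (Protocol Table 9) may use local collection, and the scheduled chemistry visits are four weeks apart. Many of those repeats would therefore fall between scheduled visits.

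**2. Effect on a summary.** Suppose local results exceed central results by a constant *b*. A change with a central baseline and a local follow-up is shifted by +*b*; the reverse pairing is shifted by −*b*; same-source pairs are not shifted. If *k* of *n* participants at a visit have a central baseline and a local follow-up, and the rest are same-source, the mean change moves by *k* × *b* / *n*. The documents give neither *b* nor *k*, so no size can be stated.

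**3. The obvious alternative for chemistry.** The alternative is to use central when reportable and local otherwise.

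| | Local-first (SAP) | Central-first |
|---|---|---|
| Both results at a visit | Local value in table | Central value in table |
| Only local reportable | Local value in table | Local value in table |
| Mixed-source changes possible | Yes | Yes, wherever the central sample fails |
| Local result that drove a decision | In table | Out of table if a central value exists |

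Central-first removes source switches only at visits with both results. Protocol 8.4.5 and the footnote to Table 7 both recognize that hemolysis from the disease itself can prevent central testing. Each ordering has a cost, and neither ensures same-source changes.

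**4. Hematology passages side by side.** Protocol 8.4.5 gives central as the general rule. Footnotes a and b of Table 11 qualify it for hematology, though footnote b names no laboratory. SAP 9.3.1 says local. Within the SAP, the hematology item and the tie-break both point to local, so the SAP gives one consistent instruction. On ranges, the low/normal/high tabulation applies wherever ranges are available, and a result would ordinarily be classified against the range of the laboratory that produced it.

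**The case for a change.** The strongest argument for a change is that the SAP text is mandatory and unrestricted. Tying the tie-break to the two listed exceptions does not narrow it much, because the participant-management exception can cover any test the investigator finds necessary. If local-first is intended, the opening central-laboratory sentence is inaccurate; if it is not, the tie-break is. On hematology, the footnotes sit beside the central rule without reversing it. A few sentences and a source flag would settle all of this cheaply.

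Part of that stands. The opening sentence of SAP 9.3.1 is looser than the rule that follows it, the laboratories named for hematology do differ, and event-driven local testing is plausibly not random across participants.

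The rest carries less weight:

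- Table 3.3.2 is titled as chemistry values with no central label. Table shells are in a separate document, so one cannot say readers would be misled.
- SAP 11.1 covers changes to protocol-defined analyses. Protocol 10.3.3 names no laboratory source for the safety summaries and plans no formal comparison of laboratory data. Where a panel was run is study conduct.
- COVID-19 travel restrictions are among the reasons for local testing, and in those cases there may be no competing central sample.
- A source flag would be presentational. The visible list of listings stops after the 6-minute walk test, so whether a laboratory listing already shows the source cannot be checked.
- Hemoglobin belongs to the hematology panel, so the same question touches the response summary. That summary is also descriptive, and nothing in the documents shows that any participant's classification would differ.

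**Conclusion.** No change to the plan follows. The chemistry rule is a workable default with exceptions and a tie-break, and the choice between local-first and central-first is a fair trade-off that belongs to the sponsor. The hematology mismatch between Protocol 8.4.5 and SAP 9.3.1 is genuine but clerical. Resolving it would record which laboratory was used without altering a computed value, and analysts can fill the gap on reference ranges sensibly.

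The reach is at most 78 chemistry and 78 to 117 hematology participant-visits in the double-blind period. The effect on any summary is unknown and cannot be derived from the documents. What remains concerns the labeling and interpretation of descriptive tables for 13 participants in a terminated study with no p-values or comparisons.

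This rests on two assumptions: that the laboratory data identify the source of each result, and that each result is classified against the ranges of the laboratory that produced it. A demonstrated systematic difference between local and central assays, together with many visits holding both results, would be a reason to reconsider. The documents show neither.
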